#### 14.2. Sample Size Justification

Approximately 50 eligible subjects will be enrolled to target approximately 40 subjects to complete the study. The sample size was calculated to test both the primary hypothesis with a 2-sided type I error of 5% and a minimum of power of 80%.

Based on historical data from [REDACTED] where the same Test lens was utilized, the proportion of eye at lens fitting for distance monocular high luminance high contrast was 0.995 and the correlation between the left and right eyes was 0.627. Using this information the total number of subjects needed to achieve the primary hypothesis is 34 subjects. To account for subject dropout this study will target to enroll approximately 50 subjects with the aim to complete approximately 40 subjects.

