### 14.5. Primary Analysis

#### Visual Acuity (logMAR)

Distance monocular high luminance high contrast visual acuity data will be dichotomized into two groups where  $Y=1$  if subjects VA is below 0.176 logMAR and  $Y=0$  otherwise;  $Y$  will be analyzed using a generalized linear mixed model with the logit as the link function. Sequence of lens wear, study period and lens type will be included in the model as fixed effects. Other characteristics such as age may be included as covariates in the model. Site will be included as a random effect (G-side). The covariance between residual errors from the same subject and eye across study periods will be modeled using either homogenous compound symmetry (CS) or unstructured (UN). The structure that returns the lowest finite-sample corrected Akaike's Information criterion will be selected as the structure that best fits the model. The Kenward and Roger method, will be used for the denominator degrees of freedom. The proportion of eye with 0.176 logMAR or better while wearing the Test lens will be estimated using a 95% confidence interval for the estimated proportion.

The null and alternative hypothesis to test for superiority of the Test relative to the pre-defined threshold 0.176 logMAR is as follows:

$$H_o: P_{Test} \leq 90\%$$
$$H_A: P_{Test} > 90\%$$

Superiority will be declared if the lower limit of the 95% confidence for the estimated proportion of eyes with distance monocular high luminance high contrast VA better than 0.176 logMAR while wearing the Test lens is above 90%. i.e.  $P(p_{Test} > 90\%) \geq 0.975$ .

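### The primary logit model omits the between-eye correlation, has no fallback when no Test eye fails, and picks its covariance by an AICc comparison that is not valid for it

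*Combined protocol and SAP*

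**What the plan says.** In section 14.5 (Primary Analysis), high-luminance, high-contrast acuity is dichotomised at 0.176 logMAR and "will be analyzed using a generalized linear mixed model with the logit as the link function". Sequence, period and lens are fixed effects, and site is a G-side random effect. Covariates are optional: "Other characteristics such as age may be included as covariates in the model". The dependence that is modelled is the "covariance between residual errors from the same subject and eye across study periods", as compound symmetry (CS) or unstructured (UN). The one used is "The structure that returns the lowest finite-sample corrected Akaike's Information criterion". Degrees of freedom follow Kenward-Roger, whose cited source is by its title a restricted maximum likelihood method. The Test lens succeeds if the lower 95% limit for its proportion of eyes exceeds 90%.

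Section 14.2 assumes a success proportion of 0.995 and states that "the correlation between the left and right eyes was 0.627". It gives 34 subjects as needed, with about 50 to be enrolled and about 40 to complete.

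Section 14.1 names SAS 9.4 but no procedure or estimation method. Section 14.7 uses the same AICc rule for the linear CLUE model. No section says what is done if the primary model cannot be fitted.

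**The concern.** One lower confidence limit decides this confirmatory trial, and the covariance model sets its standard error and degrees of freedom. Three features of that model need attention.

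1. **Selection rule.** AICc ranks structures only when both are fitted to the same data with a proper likelihood. That is true of the linear CLUE model. A residual covariance on a binary logit outcome defines no joint likelihood.
2. **Clustering.** Each subject contributes two Test eyes in one period. If the covariance block is one eye over two periods, the two eyes are treated as independent given site, and the interval is too narrow.
3. **Separation.** At a success rate of 0.995 there may be no failing Test eye at all. The Test-lens logit is then unbounded, and there is no finite standard error to build a limit from.

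**Working it through.** **A. Is AICc comparable across CS and UN?** Laplace and quadrature fits cannot take a residual-side covariance, and Kenward-Roger rests on REML. What remains is linearisation: the model is fitted to a pseudo-response, eta + (y - mu)/[mu(1 - mu)], which is rebuilt as the fit proceeds and so depends on the structure being fitted.

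UN contains CS. On common data, -2 log L for UN can therefore never exceed that for CS. This was tested by simulating a restricted pseudo-likelihood fit with 40 subjects, two eyes and two periods. Assumptions not in the documents: latent correlation 0.85, one age-like covariate, site omitted.

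| Block | True proportion | Both converged | UN worse than nested CS | CS/UN choice changed when pseudo-data held fixed |
|---|---|---|---|---|
| Eye (2 records) | 0.95 | 35 of 60 | 25 | 10 |
| Eye (2 records) | 0.90 | 56 of 60 | 48 | 15 |
| Subject (4 records) | 0.95 | 16 of 60 | 4 | 4 |
| Subject (4 records) | 0.90 | 34 of 60 | 21 | 20 |

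The impossible ordering is common, so the criteria do not refer to the same data. With complete balanced data, no covariate and no site effect, the pseudo-data are identical and AICc picks CS on its penalty alone.

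**B. Does the choice move the decision limit?** A similar simulation (eye-level block, fixed t of 2.02 in place of Kenward-Roger) compared the lower 95% limit for the Test proportion under CS and UN.

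- True proportion 0.90, 122 converged fits: median absolute difference 0.0004, 90th percentile 0.004.
- True proportion 0.95, 77 converged fits: 0.0003 and 0.003.
- The comparison with 90% changed in 0 of 122 + 77 = 199 fits. One run differed by 0.63 without changing the decision.

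**C. Omitted between-eye correlation.** With two eyes per subject, the variance of the Test proportion is p(1 - p)/(2n) × (1 + 0.627). Ignoring the correlation gives a standard error of 1/√1.627 = 0.784 of the correct one, about 22% too small.

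Consequence at the null, p = 0.90, with 40 subjects (80 Test eyes), in a simplified one-sample calculation without period, sequence or site:

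- Both eyes fail: 0.1² + 0.627 × 0.09 = 0.06643. One fails: 2 × 0.09 × 0.373 = 0.06714. Neither fails: 0.86643.
- A logit Wald interval treating eyes as independent has lower limit 0.917 with 1 failing eye, 0.906 with 2 and 0.890 with 3. It passes with 1 or 2.
- P(1) = 40 × 0.86643³⁹ × 0.06714 = 0.0100.
- P(2) = 40 × 0.86643³⁹ × 0.06643 + 780 × 0.86643³⁸ × 0.06714² = 0.0099 + 0.0151 = 0.0250.
- False success: 0.0100 + 0.0250 = 3.5%, against the 2.5% allowed.

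A separate simplified check gave about 3.4%, against 2.5% with subject clustering. The excess depends on n because the counts are discrete: the same enumeration gives 2.0% with 34 subjects and 3.0% with 50.

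**D. No failing Test eye.** At p = 0.995:

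- P(both eyes succeed) = 0.995² + 0.627 × 0.995 × 0.005 = 0.99314.
- P(no failing Test eye): 0.99314³⁴ = 0.791, 0.99314⁴⁰ = 0.759, 0.99314⁵⁰ = 0.709.
- Expected failing Test eyes with 40 subjects: 80 × 0.005 = 0.4.

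In a simulation at 0.995 with no covariate, none of 60 data sets gave a usable fit: 45 had no failing eye and 15 did not converge.

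**E. Would a fallback give an answer?** With no failing eye, the exact lower limit on the effective number of eyes is 0.025^(1.627/2n). This is 0.916, 0.928 and 0.942 for n = 34, 40 and 50. All exceed 0.90, so the trial can be decided in exactly the case where the logit model gives nothing.

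**The case against.** The strongest reply is that the AICc flaw does no harm. Part B supports this: in converged fits the limits nearly coincide, and UN adds only one parameter to CS in a two-period block. A reader might infer that the selection rule makes the decisive limit arbitrary; nothing in the plan or the simulations shows that. Nor do the documents say that the fit is by pseudo-likelihood, or that the rule was copied from the CLUE model. The first is an inference from the elements specified, although I know of no fit that keeps them all and has a true likelihood. The second is only a resemblance of wording.

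It is also fair to say that the 71% to 79% figures are not evidence against AICc. They describe separation, which defeats a logit model under any covariance structure. Nor does an absence of Test failures remove all information on covariance, because Control eyes are in the same model. Those eyes do not, however, bound the Test-lens logit.

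On the between-eye point, the wording could be meant as a four-record block per subject. That reading is possible but not the natural one, and the text needs settling either way.

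Finally, section 14.10 requires any change of analysis to be documented and justified. That is useful, but it leaves the replacement method to be chosen after the data are seen.

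**Conclusion.** The point stands, with its weight on clustering and separation. Lowest AICc is not a valid way to choose the residual covariance of this model, but its effect on the decision limit appears small when the model converges. That finding rests on an assumed latent correlation of 0.85, one covariate, no site effect and no Kenward-Roger adjustment.

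If the covariance is read as same eye across periods, the standard error is about 22% too small under the plan's own 0.627. False success at a true 90% is then about 3.5% with 40 subjects instead of at most 2.5%, a modest excess that varies with n.

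Under the plan's own 0.995 and 0.627, the specified model gives no usable lower limit in roughly 71% to 79% of trials for want of a failing Test eye, and no alternative is stated. This is the most consequential of the three, since it is the scenario for which the trial was sized.

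**What to change.** In section 14.5:

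- Delete the AICc selection and prespecify one marginal method clustered on subject, covering both eyes and both periods. An example is GEE with an exchangeable working correlation and a small-sample-corrected robust variance.
- State a fallback for the Test proportion: a cluster-adjusted exact or Wilson interval, used when there are no failing Test eyes, when failures number at or below a count fixed in advance, or when the model does not converge. Fix the correlation for the adjustment in advance as well (0.627 is the plan's own value), because data with no failures cannot estimate it.
- Do not substitute a subject random intercept unless the proportion is marginalised. The hypothesis concerns a population proportion of eyes. With a logistic random intercept, a marginal 90% corresponds to a conditional 97.4%, 98.6% or 99.8% for assumed latent intraclass correlations of 0.60, 0.70 or 0.85. Comparing that conditional value with 90% could declare success falsely.
- Keep the 90% decision rule, and keep AICc for the linear CLUE model in section 14.7.

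The cost is a paragraph of SAP text and a few lines of code. The interval may be somewhat wider than under the model as written.

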### 2.3. Hypotheses

#### Primary Hypothesis

1. The proportion of eyes with corrected distance monocular visual acuity 0.176 logMAR or better (ie, Snellen VA 20/30 or better) using the Test lenses under high illumination/high contrast is superior to 90%.

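### The 80% power in Section 14.2 does not belong to the Section 14.5 analysis, which at the plan's own inputs gives a finite Test-lens estimate in under 2% of trials

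*Combined protocol and SAP*

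**What the plan says.** The only confirmatory hypothesis (Section 2.3) is that the proportion of eyes at 0.176 logMAR or better "using the Test lenses under high illumination/high contrast is superior to 90"%.

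Section 14.2 sizes the study for "a 2-sided type I error of 5% and a minimum of power of 80"%. Its inputs are historical. For the pass rate it reports that "the proportion of eye at lens fitting for distance monocular high luminance high contrast was 0.995". For the dependence within a subject it reports that "the correlation between the left and right eyes was 0.627". From these it concludes that "the total number of subjects needed to achieve the primary hypothesis is 34 subjects", and it plans about 40 completers from about 50 enrolled. Text run into the Section 14.3 heading names the POWER procedure. No simulation or model-based power calculation is described.

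Section 14.5 specifies the analysis. The pass/fail outcome "will be analyzed using a generalized linear mixed model with the logit as the link function", with sequence, period and lens fixed, site random, and compound-symmetric or unstructured residual covariance. "Superiority will be declared if the lower limit of the 95% confidence for the estimated proportion of eyes" that pass with the Test lens is above 90%. The section does not state the scale on which the limit is built, what happens if a cell has no failing eye, or how the two high-contrast chart reads per eye (Section 7.2, steps 1.23 and 3.11) become one outcome.

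**The concern.** When almost every eye is expected to pass, a logit model has very few failures to work with, and this model splits them across the two sequence-by-period cells in which the Test lens is worn. A cell without failures has no finite logit. Where both cells do have failures, a logit-scale standard error near 100% is so large that the lower limit may stay below 90%. If so, a lens performing exactly as assumed would almost always fail to meet the primary hypothesis, and the stated power would describe a test that the plan does not use.

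**Working it through.** **Inputs.** Null 0.90 (Section 2.3). Assumed proportion p = 0.995, correlation ρ = 0.627, two-sided 5%, 34 required, 40 planned completers (Section 14.2). Equal allocation in blocks of 2 (Section 5.1). Assumed here: one row per eye per period, no site variance, no extra covariates.

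**1. Reproducing 34.** Take the subject-level event that both eyes pass, with probability p² + ρp(1−p):
- at 0.90: 0.81 + 0.627 × 0.09 = 0.8664
- at 0.995: 0.990025 + 0.627 × 0.004975 = 0.9931

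A one-sample z test then needs n = [(1.960√(0.8664 × 0.1336) + 0.842√(0.9931 × 0.0069)) / (0.9931 − 0.8664)]² = 33.76, so 34, with power 80.9%. The plan does not give its formula. This was the only variant tried that uses all the stated inputs and gives 34. An eye-level z test with design effect 1.627 gives 39 subjects. None of these is the Section 14.5 analysis.

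**2. The Test estimate in Section 14.5.** Intercept, sequence, period and lens are four parameters for the four cells of a 2×2 crossover. The Test mean is therefore the average of the two Test-cell logits. With x₁ and x₂ failing eyes of n eyes per cell (n = 34 at 34 subjects, 40 at 40 subjects):
- estimate = ½[ln((n−x₁)/x₁) + ln((n−x₂)/x₂)]
- variance = ¼[1/x₁ + 1/(n−x₁) + 1/x₂ + 1/(n−x₂)]

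Both are finite only if x₁ and x₂ are at least 1. Trial fits with one cell free of failures gave a standard error above 6000 and a lower limit of 0.

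**3. How often it is finite.** Let g = P(both eyes pass) = 0.9931.
- 34 subjects: a Test cell has no failures with probability g¹⁷ = 0.890, so both cells have one with probability (1 − 0.890)² = 1.2%.
- 40 subjects: g²⁰ = 0.871, so (1 − 0.871)² = 1.7%.

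**4. The limit when it is finite**, on the logit scale and back-transformed. The range runs from t on N−2 df to z.

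| Subjects | Failing eyes per Test cell | Estimate | SE | Lower limit |
|---|---|---|---|---|
| 34 | 1 and 1 | 3.497 | 0.718 | 0.884–0.890 |
| 40 | 1 and 1 | 3.664 | 0.716 | 0.901–0.906 |
| 40 | 1 and 2 | 3.304 | 0.623 | 0.885–0.889 |
| 40 | 2 and 2 | 2.944 | 0.513 | 0.871–0.874 |

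For the first row with z: 3.497 − 1.960 × 0.718 = 2.090, which back-transforms to 0.890. No pattern passes at 34, and only 1-and-1 passes at 40. A subject-clustered standard error (0.892 for 1-and-1 at 34; 0.891 for 1-and-2 at 40) does not change this.

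**5. Chance of meeting the rule**, counting a non-estimable result as no success. Let d = P(exactly one eye fails) = 2 × 0.995 × 0.005 × 0.373 = 0.00371. At 40 subjects P(1-and-1) = [20 d g¹⁹]² = [20 × 0.00371 × 0.8775]² = 0.0042, or 0.4%. At 34 it is 0. The same formula at a true rate of 0.90 gives 0.8%, so a lens on the null boundary would meet the rule more often than the expected lens.

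**6. An exact rule at 40 subjects: at most 1 of 80 Test eyes fails.**
- Power: g⁴⁰ + 40 d g³⁹ = 0.759 + 0.114 = 87.3%.
- Type I error at 0.90: 1.3% at ρ = 0.627, and at most 1.8% for any ρ from 0 to 1.
- If Section 14.5 is kept and this rule is used only when a Test cell has no failing eye, the 1-and-1 pattern is added: 87.3% + 0.4% = 87.7% power. Type I error is 1.3% + 0.8% = 2.1% at ρ = 0.627, and at most 2.2% for any ρ (logit-scale limit).
- At 34 subjects with ρ = 1, even zero failures has type I error 0.9³⁴ = 2.8%.

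**The case against.** Several points against the concern have force.

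- **A fallback would restore the power.** A reader might infer that a fallback for non-estimable fits would not help, because fitted cases still lose. That is not so. Nearly all the loss is non-estimability, and step 6 shows that a fallback alone brings power at 40 subjects to about 87.7%. But the plan contains no fallback.
- **The interval scale is unstated.** A reader might infer from step 4 that the rule can never be met at 34. That needs a logit-scale limit. A delta-method limit on the proportion gives 0.930 for 1-and-1 and 0.909 for 1-and-2 at 34, and 0.902 for 2-and-2 at 40. The scale does not change how rarely the estimate is finite.
- **One row per eye is an assumption.** With one row per chart read and a naive standard error, one failing read per Test cell at 34 subjects would give 0.943. A subject-clustered standard error would shrink that gain.
- **34 is the calculated requirement, not the plan.** The plan is 40 completers from 50 enrolled. Because the endpoint is read at fitting, the analysed number may exceed 40. At 50, the 1-and-1 and 1-and-2 patterns pass (0.924 and 0.910), yet the chance of meeting the rule is still only 1.7%.
- **Sequence and period could be dropped.** One failing eye in 68 would then reach 0.903 with z (0.896 with t on 33 df), but this contradicts Section 14.5.
- **The rule is also written as a probability statement about the proportion.** No prior is given, and the information criterion and Kenward-Roger degrees of freedom are frequentist.

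A reader might also infer that the random site effect removes the one winning pattern. The documents do not give the number of sites and no site model was fitted, so nothing is claimed about it.

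**Conclusion.** The concern holds in this form: the 80% in Section 14.2 is not the power of the Section 14.5 rule. At the plan's inputs, with one row per eye and non-estimable results counted as no success, the chance of meeting the rule at 40 completers is at most 1.7% whatever the interval scale, and about 0.4% with a back-transformed logit limit. Non-estimability accounts for most of the loss, and the ceiling on the logit limit adds to it. The documents do not support saying that success is impossible. Because this is the only confirmatory hypothesis, the mismatch should be settled before the data are unmasked.

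**What to change.** Base the primary decision on the observed Test-lens proportion, with an exact rule that allows for between-eye correlation. With 40 subjects read on the Test lens, declare success if at most 1 of 80 Test eyes fails. For another number, use the largest count of failing eyes that keeps type I error at or below 2.5% for every correlation from 0 to 1. Two ways of adopting it are acceptable:

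1. Replace the model-based limit and keep the logit model as descriptive.
2. Keep Section 14.5 and prespecify the exact rule for whenever a Test cell has no failing eye. The 2.2% bound on type I error was computed for a logit-scale limit and must be redone for any other scale.

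In either case, state how the two chart reads per eye are combined and the scale of any model-based interval. Restate the power and required number in Section 14.2 for the rule adopted. The figure of 34 cannot stand under the exact rule, because at that number no cutoff holds 2.5% at every correlation.

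The cost is SAP wording and a restated power statement. At the planned 40 completers, no extra subjects or data are needed.

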### 14.6. Secondary Analysis

Not applicable.

### 14.7. Other Exploratory Analyses

Further statistical exploratory analysis can be undertaken, if necessary, at the discretion of the clinical project leader.

Methods for CLUE will follow the analysis described below:

#### CLUE Scores

CLUE scores will be analyzed separately by domain using a linear mixed model adjusting for baseline values as a covariate. Sequence of lens wear, study period and lens type. Other characteristics such as race, gender and age may be included in the model as covariates. Site will be included as a random effect (G-side). The covariance between residual errors from the

# Clinical Study Protocol

## Johnson & Johnson Vision Care, Inc.

same subject across study periods will be modeled using either homogenous compound symmetry (CS) or unstructured (UN). The structure that returns the lowest finite-sample corrected Akaike's Information criterion will be selected as the structure that best fits the model. The Kenward and Roger method, will be used for the denominator degrees of freedom.

Comparisons between the Test and Control will be carried out using 2-sided 95% confidence intervals constructed for the least-square means (Test minus Control) at the 1-week follow-up evaluation. The null and alternative hypothesis for CLUE vision scores to test for non-inferiority of the Test lens relative to the Control lens is as follows:

$$H_0: \mu_{Test} - \mu_{Control} \leq -5$$
$$H_A: \mu_{Test} - \mu_{Control} > -5$$

Non-inferiority will be declared if the lower limit of the 95% confidence interval for the least-square mean difference is greater than -5. i.e.  $P(\mu_{Test} - \mu_{Control} > -5) \geq 0.975$ .

### 14.8. Interim Analysis

An interim analysis will be conducted after 20 patients have completed the study, in order to monitor the safety and efficacy of the study lenses. Only descriptive statistics will be provided to the study responsible clinician and the project lead. No statistical analyses will be performed during the interim read. No stopping rules will be applied.

### 14.9. Procedure for Handling Missing Data and Drop-Outs

Missing or spurious values will not be imputed. The count of missing values will be included in the summary tables and listings.

Subject dropout is expected to be one of the main reasons of missing data in this clinical trial. Past clinical trials don't provide the evidence that subject dropout is systematic or not-at-random. To evaluate the impact of missing data, sensitivity analysis will be conducted using multiple imputation methods if the proportion of subject dropout is greater than the 15%. The SAS/STAT procedures PROC MI and PROC MIANALYZE will be utilized with a parametric regression method used to make at least 15 imputations.

### 14.10. Procedure for Reporting Deviations from Statistical Plan

The analysis will be conducted according to that specified in above sections. There are no known reasons for which it is planned to deviate from these analysis methods. If for any reason a change is made, the change will be documented in the study report along with a justification for the change.

